9.6.3 Electrocardiogram

Twelve-lead ECG will be performed at the following time points during the study:

- Week 1 (prior to and 30 minutes following end of infusion) (if required)
- Monthly (Week 4, Week 8, etc) (prior to and 30 minutes following end of infusion)
- 1-Week Post-treatment Follow-up
- 4-Week Post-treatment Follow-up

Additional ECG assessments will be performed for patients with evidence of generalized IRR. These data will be listed, but not summarized. The results of the 12-lead ECGs will be summarized using descriptive statistics for each assessment for actual and CFB values. Corrected QT intervals using Bazett's and Fridericia's correction will be provided. The following formulas will be used:

- $QTcB = QT / ([RR/1000]^{1/2})$
- $QTcF = QT / ([RR/1000]^{1/3})$

All ECG data will be listed, both for quantitative data and for overall interpretation.

9.6.4 Vital Signs

Vital signs, including systolic and diastolic blood pressure, heart rate, respiration rate, and body temperature will be assessed at every visit. On dosing days, vital signs will be measured prior to, every 30 minutes during the infusion, at the end of infusion, and 30 minutes after the end of infusion.

Additional vital sign assessments will be performed for patients with evidence of generalized IRR. These data will be listed, but not summarized. Vital sign results will be summarized using descriptive statistics for each assessment for actual and CFB values as well as for change from pre-infusion values.

All vital sign data will be listed together with body weight.

9.6.5 Physical and Neurological Examinations

Complete physical and neurological examinations will be performed at Week 1 (if required), every 6 weeks (Week 6, Week 12, etc), and 4-Week Post-treatment Follow-up. Additionally, physical examinations may be performed at any time during the study, as clinically indicated.

All physical and neurological examinations data will be listed.

9.6.6 Pulmonary Evaluations

9.6.6.1 Pulmonary Function Tests (PFTs)

The following PFTs will be measured at Week 1 (if required), every 6 weeks (Week 6, Week 12, etc), and 4-Week Post-treatment Follow-up:

- FEV₁

- FVC
- FEV₁/FVC ratio

The following PFTs will be measured at Week 1 (if required), every 3 months (Week 12, Week 24, etc), and 4-Week Post-treatment Follow-up:

- Total lung capacity
- DLCO

Additional PFT assessments will be performed for patients with evidence of generalized IRR. These data will be listed, but not summarized. PFT results will be summarized using descriptive statistics for each assessment for actual, CFB values, and percent CFB values.

All PFT data will be listed.

9.6.6.2 Pulse Oximetry

Oxygen saturation (SpO₂) will be monitored continuously via pulse oximetry from 5 minutes prior to infusion until 30 minutes after the end of infusion on all dosing days. Oxygen saturation pre-infusion will be summarized using descriptive statistics for each visit. The number and percentage of patients with post-infusion SpO₂ levels below 95% will be provided for each visit. Additional pulse oximetry assessments will be performed for patients with evidence of generalized IRR. These data will be listed, but not summarized.

Percent change from pre-infusion (CFB) will be calculated for SpO₂ values that fall below 95% as $[(\text{post-infusion SpO}_2 - \text{pre-infusion SpO}_2) / \text{pre-infusion SpO}_2] * 100$.

Pulse oximetry data will be listed. Percent CFB for SpO₂ values that fall below 95% will be provided in the listing. Additionally, SpO₂ values that fall below 88% and/or have a > 5% in percent CFB will be flagged in the listing.

9.6.7 Immunogenicity Analyses

Samples for ADA titers will be collected at Week 1 (if required), every 6 weeks (Week 6, Week 12, etc), 1-Week Post-treatment Follow-up, 4-Week Post-treatment Follow-up, and 12-Week Post-treatment Follow-up. Samples for Jo-1 Ab will be collected weekly (Week 1, Week 2, Week 3, etc), 1-Week Post-treatment Follow-up, 4-Week Post-treatment Follow-up, and 12-Week Post-treatment Follow-up. Samples will also be collected for patients experiencing generalized IRRs. These data collected for IRRs will be listed, but not summarized. Only samples collected at the defined sample collection time points will be provided in summary tables. Tables will summarize the maximum ADA titer and Jo-1 Ab signal observed per individual. ADA titers and Jo-1 Ab qualitative results will be listed.

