The completed healthy volunteer study included 24 healthy subjects who tested negative for antibodies against HARS (i.e., Jo-1 antibody [Ab]) exposed to a single IV dose of ATYR1940 in a Phase 1, first-in-human, randomized, double blind, placebo-controlled, single ascending dose study (ATYR1940-C-001). In this study, ATYR1940 was investigated at doses of 0.1, 0.3, 1.0, and 3.0 mg/kg. Within each dose cohort, 6 subjects received ATYR1940 and 2 subjects received placebo. A single, 30-minute IV infusion of

ATYR1940 0.1 to 3.0 mg/kg was safe and well tolerated by healthy subjects. All adverse events (AEs) were mild in severity, non-serious, and transient. Overall, treatment-emergent AEs (TEAEs) reported for more than 1 ATYR1940-treated subject included dizziness, headache, abdominal distension, fatigue, nasopharyngitis, nausea, and oropharyngeal pain. No dose relationship was apparent with regard to the occurrence of these AEs. Furthermore, no clinically relevant changes from baseline in safety laboratory tests, vital signs, electrocardiograms (ECGs), pulmonary function tests (PFTs), or arterial oxygen saturation (based on pulse oximetry) were observed. Six ATYR1940-treated subjects were determined to be anti-drug-antibody (ADA) positive at at least one post-dose time point; one of these subjects also was ADA positive at baseline. ADA positivity was not associated with any temporal adverse systemic symptoms, safety laboratory abnormalities, or abnormal spirometry or pulse oximetry findings in any of these subjects. Furthermore, the pharmacokinetics (PK) of ATYR1940 was not altered in these subjects.

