9.2.8. Safety Analysis

9.2.9. Safety and Immunogenicity Analyses

Safety evaluations will be based on the incidence, type, and intensity of AEs, and changes from baseline in safety laboratory tests, ECG findings, vital signs measurements, PFTs, and pulse oximetry. Immunogenicity will be assessed based on the incidence of infusion site reactions, ADA titers, changes in Jo-1 and ADA titers over time, as appropriate, as well as changes from baseline over time in immune-based laboratory tests, including, for example, tryptase, complement factors, and cytokines. Safety variables will be tabulated and presented for all patients who receive any amount of study drug and have follow-up safety data. Tabulations will be presented for safety data overall and separately for the parent and extension studies.

AEs will be coded using the current version of the Medical Dictionary for Regulatory Activities (MedDRA) for purposes of summarization. The overall incidence of AEs occurring during the study will be summarized by MedDRA system organ class and preferred term. The incidence of TEAEs also will be summarized by system organ class

and preferred term. For the purpose of analysis, a TEAE is defined as any AE that occurs after administration of the first dose of ATYR1940 through the 12-week posttreatment follow-up visit, or any event that is present at baseline, but worsens in intensity or is subsequently considered drug-related by the Investigator. Severe TEAEs, SAEs, and discontinuation rates of study therapy due to TEAEs also will be summarized.

Events that are considered related to treatment (possibly, likely, or definitely drug-related) will also be tabulated. A tabulation will also be provided that enumerates TEAEs by maximum severity. Deaths, SAEs, and TEAEs resulting in study discontinuation will be tabulated, if warranted by the data.

All AEs occurring on study will be listed in by-patient data listings.

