4.1.2 Immunogenicity Variables

Immunogenicity will be evaluated based on the following variables:

- Anti-drug antibody (ADA) titers
- Jo-1 antibody (Ab) seroconversion

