14.2.6 IMMUNOGENICITY DATA TABLES

14.2.6.1 Maximum Individual Anti-drug Antibody (ADA) Titers (Safety Population 006)

Disease	Number Screened Positive	Confirmed Positive Overall	Confirmed Positive		
			41≤Titer≤328	656≤Titer≤2,624	Titer>2,624
Total (N = xx)	x	x	x	x	x
EO-FSHD (N = xx)	x	x	x	x	x
FSHD (N = xx)	x	x	x	x	x
LGMD2B (N = xx)	x	x	x	x	x

Note: FSHD=Facioscapulohumeral muscular dystrophy; LGMD2B=Limb-girdle muscular dystrophy 2B; EO-FSHD=Early Onset Facioscapulohumeral muscular dystrophy
Source: Listing xx.x.xx, Dataset: [NAME], Program: xxxxxx.sas, Output: T_14_2_6_1_XXXXX.rtf, Generated on: DDMMYYYY HH:MM
Page x of y

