14.2.6.2 Maximum Individual Anti-drug Antibody (ADA) Titers (Safety Population Cumulative)

Disease	Number Screened Positive	Confirmed Positive Overall	Confirmed Positive		
			41≤Titer≤328	656≤Titer≤2,624	Titer>2,624
Total (N = xx)	x	x	x	x	x
EO-FSHD (N = xx)	x	x	x	x	x
FSHD (N = xx)	x	x	x	x	x
LGMD2B (N = xx)	x	x	x	x	x

Note: FSHD=Facioscapulohumeral muscular dystrophy; LGMD2B=Limb-girdle muscular dystrophy 2B; EO-FSHD=Early Onset Facioscapulohumeral muscular dystrophy

Source: Listing xx.x.xx, Dataset: [NAME], Program: xxxxxx.sas, Output: T_14_2_6_2_XXXXX.rtf, Generated on: DDMMYYYY HH:MM
Page x of y

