14.2.6.3 Maximum Individual Jo-1 Ab Levels (Safety Population 006)

Disease	Jo-1 (U/ml)			
	0≤Jo-1≤0.5	0.5<Jo-1<1.5	1.5≤Jo-1<5	Jo-1≥5
Total (N = xx)	x	x	x	x
EO-FSHD (N = xx)	x	x	x	x
FSHD (N = xx)	x	x	x	x
LGMD2B (N = xx)	x	x	x	x

Note: FSHD=Facioscapulohumeral muscular dystrophy; LGMD2B=Limb-girdle muscular dystrophy 2B; EO-FSHD=Early Onset Facioscapulohumeral muscular dystrophy

Source: Listing xx.x.xx, Dataset: [NAME], Program: xxxxxx.sas, Output: T_14_2_6_3_XXXXX.rtf, Generated on: DDMMYYYY HH:MM
Page x of y

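### The ADA and Jo-1 tables band each patient's maximum without reference to baseline, so ADA arising on treatment cannot be counted, and Jo-1 seroconversion is neither defined nor tabulated

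*SAP*

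**What the plan says.** Immunogenicity belongs to the first study objective. Protocol 3.2.1 lists the incidence and level of ADA and Jo-1 antibody among the safety endpoints. Protocol 9.2.9 adds "changes in Jo-1 and ADA titers over time", qualified by the words as appropriate. SAP 4.1.2 names two immunogenicity variables: ADA titres and "Jo-1 antibody (Ab) seroconversion".

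For the summaries, SAP 9.6.7 says "Tables will summarize the maximum ADA titer and Jo-1 Ab signal observed per individual". It also says "Only samples collected at the defined sample collection time points will be provided in summary tables", which leaves out samples taken because of an infusion-related reaction but not pre-dose samples.

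The shells follow this rule:
- **ADA (Tables 14.2.6.1 and 14.2.6.2):** columns for screened positive, confirmed positive and three titre bands.
- **Jo-1 (Tables 14.2.6.3 and 14.2.6.4):** four bands, namely 0 to 0.5, above 0.5 to below 1.5, 1.5 to below 5, and 5 U/mL or more.

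Each pair is produced once on 006 data alone and once on parent plus 006 data. Rows are disease groups and cells are counts. SAP 6.0 sets the parent-study baseline as baseline for everyone, but none of these four tables uses it.

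**The concern.** Every 006 patient has already completed treatment in a parent study, so antibody found in 006 can have three origins: before any ATYR1940, during the parent study, or during 006. A maximum that ignores baseline merges them. Incidence, in the ordinary sense of new occurrence, needs the first group removed, and a statement about long-term treatment needs the second separated from the third.

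Pre-existing ADA does occur. Protocol 2.3 says of the ADA-positive healthy volunteers that "one of these subjects also was ADA positive at baseline". The SAP gives haematology, chemistry, ECG, vital signs and pulmonary function a parent baseline and change in their tables, and haematology and chemistry also get shift tables. Immunogenicity gets neither. Section 1.1 of the SAP, which records changes from the protocol, does not mention leaving out a summary of change over time.

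**Working it through.** The plan gives no figure on this point, so there is nothing to reproduce. The check is of what the tables can distinguish, with arithmetic for scale only.

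**1. Can the pair of ADA tables recover the origin?** Consider four ADA histories:

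| History | Counted positive in 006 table | Counted positive in cumulative table |
|---|---|---|
| Positive before any dose, persists into 006 | yes | yes |
| First positive in parent study, persists into 006 | yes | yes |
| First positive in 006 | yes | yes |
| Positive at parent baseline or in parent study only, negative throughout 006 | no | yes |

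The first three rows are identical, so subtracting one table from the other isolates only antibody that had gone before 006. The result does not depend on whether a Week 1 pre-dose sample is counted, because antibody that persists to Week 6 enters the maximum anyway.

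**2. Does the same hold for Jo-1?** Not above the threshold. Protocol 5.2 excludes anyone who met a discontinuation criterion at any point in the parent study, and Jo-1 of 1.5 U/mL or more is one of these. The tables split at exactly 1.5. If eligibility was followed, every patient in the two upper bands, in either table, crossed 1.5 after entering 006. What cannot be resolved is a maximum below 1.5, chiefly in the 0.5 to 1.5 band. That range is not empty of interest: Protocol 7.5.5.2 says generalised infusion reactions occurred with low Jo-1 levels.

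**3. Is seroconversion reported?** It is the title of Listing 16.2.17.2, which shows result and change from baseline by patient and visit. No cut-off or definition is given, and no table carries it. The ADA listing (16.2.17.1) shows every visit but has no change column.

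**4. Scale, from the healthy-volunteer study (Protocol 2.3).**
- Treated subjects: 4 cohorts × 6 = 24. ADA positive after dosing: 6. Of those, positive at baseline: 1.
- Positive at any post-dose time: 6/24 = 25.0%.
- Newly positive among baseline-negatives: (6 − 1)/(24 − 1) = 5/23 = 21.7%, a gap of 3.3 points. This assumes no other treated subject was positive at baseline.
- Pre-existing share of positives: 1/6 = 16.7%. The baseline-positive rate 1/24 = 4.2% has a Clopper-Pearson 95% interval of 0.1% to 21.1%.

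**5. Range for 006.** Take N = 24 (the planned maximum) and an assumed pre-existing ADA rate p. Expected pre-existing positives are 24p, and P(at least one) = 1 − (1 − p)^24. If 5/23 of baseline-negatives convert and all pre-existing positives stay positive, the pre-existing share of confirmed positives is 24p / [24p + 24(1 − p) × 5/23].

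| Assumed p | Expected pre-existing | P(at least one) | Share of positives |
|---|---|---|---|
| 1% | 0.24 | 21% | 4% |
| 4.2% | 1.0 | 64% | 17% |
| 10% | 2.4 | 92% | 34% |
| 20% | 4.8 | 99.5% | 53% |

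Parent-acquired ADA is not included in this table; it would add to the mixing in the 006 counts.

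**The case against.** The best defence is that the study is descriptive, has at most 24 patients and tests no hypothesis, and that both antibodies are listed by patient and visit across parent and 006 data. A reader can trace each onset by hand. Protocol 9.2.9 asks for change over time only as appropriate, and does not fix a by-visit table as the format. The shells are headed as individual maxima and confirmed positives; they do not call the count a response or treatment-emergent.

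Much of this stands. A reader might infer that the tables present pre-existing antibody as a response; the documents do not label it so. A reader might also infer that origin cannot be separated for Jo-1 at all, or that long-term immunogenicity goes wholly unreported. The entry exclusion at 1.5 U/mL, the matching table split and the change column in Listing 16.2.17.2 rule out both.

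The volunteer figures are also limited. They come from a single dose in healthy subjects selected as Jo-1 negative, so they bear on ADA only and are not a forecast for 006.

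What the defence does not meet is the summary itself. A listing from which the incidence could be worked out is not a report of the incidence, and the ADA listing does not show change from baseline.

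**Conclusion.** The point holds in full for ADA and in part for Jo-1.

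For ADA, the planned counts cannot separate pre-existing, parent-acquired and 006-acquired antibody, so no planned table gives the incidence of ADA arising on treatment. In the one study for which the documents give counts, the difference was 25.0% against 21.7%. In 006 the pre-existing share of positives could run from about 4% to 53% for assumed pre-existing rates of 1% to 20%. These are illustrations resting on the assumptions stated with them.

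For Jo-1, the two upper bands already count crossings of 1.5 U/mL after entry, provided eligibility was followed. The defect is confined to levels below 1.5 and to a named variable that has no definition and no table.

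This affects how the immunogenicity objective is answered. It affects no test, sample size or decision rule. It should be changed because the change is cheap and the data are already held.

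**What to change.** - Restrict every maximum to samples taken after the first ATYR1940 dose: the first parent-study dose for the cumulative tables, the first 006 dose for the 006 tables.
- In the cumulative tables, cross-tabulate parent-baseline band by maximum post-first-dose band, using negative plus the three existing titre bands for ADA and the four existing bands for Jo-1. The SAP's laboratory shift tables already have this layout.
- In the 006 tables, cross-tabulate status at the last sample before the first 006 dose by maximum 006 post-dose band. SAP 9.6.7 takes ADA at Week 1 only if required, so this reference sample may have to come from the parent database.
- Report treatment-emergent ADA with baseline-negative patients as denominator.
- Define Jo-1 seroconversion in SAP 6.0 as a move from a lower to a higher existing table band relative to parent baseline, and tabulate it.

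The cost is a short definition in the SAP and revised shells. No new sample is needed, because the cumulative listings already draw on parent and 006 results. Cells will be small with up to 24 patients in three disease groups, so counts should be shown beside any percentage.

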9.7 Pharmacodynamic Analyses

9.7.1 Surveillance MRI

Surveillance skeletal muscle MRI will be conducted at Week 1 (if required), every 3 months (Week 12, 24, etc), and 12-Week post-treatment follow-up.

A listing will be generated from the surveillance MRI data showing the STIR positive muscles, the name of the muscles, the side of the body, region of the muscle (proximal, middle, and distal), and the Fischer score for that same muscle region.

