 - Pulmonary evaluations (pulmonary function tests [PFTs] and pulse oximetry).
 - Incidence and level of anti-drug antibodies (ADA) titers and Jo-1 Ab levels.
- Exploratory characterization of immune response to ATYR1940.

Muscle Effects:

- Changes from baseline in the following clinical parameters:
 - Muscle disease burden on lower extremity skeletal muscle MRI.
 - Muscle strength, based on manual muscle testing (MMT).
 - Upper and lower extremity muscle function, based on the Brooke and Vignos scales, respectively.

Pharmacodynamics (Exploratory): The PD activity of ATYR1940 will be evaluated based on the following endpoints:

- Changes in muscular-dystrophy-related inflammatory immune state in peripheral blood, as assessed by:

	
– Circulating immune proteins, such as cytokines.– Ex vivo inflammatory immune protein (including cytokines) release from peripheral blood mononuclear cells (PBMCs).– Immunophenotyping of circulating PBMCs.• Changes in serum- and/or plasma-based muscle biomarkers
Quality of Life (Exploratory):	Quality of life will be assessed, based on the Individualized Neuromuscular Quality of Life (INQoL) questionnaire and, for patients with FSHD, the FSHD-specific Health Inventory (FSHD-HI) questionnaire.
Systemic Exposure:	Systemic exposure will be determined through sparse pharmacokinetic (PK) sampling. As the data allow, PK parameters will be calculated from the drug concentration data using WinNonlin.
Sample Size Considerations:	No formal sample size calculation was performed for this extension study.
Statistical Methods:	Statistical analyses of safety, PK, and PD data will be primarily descriptive in nature. Continuous variables will be summarized using descriptive statistics (n, mean, standard deviation, median, minimum, and maximum). Categorical variables will be summarized showing the number and percentage (n, %) of patients within each classification.
Schedule of Events:	The Schedule of Events is presented in Table 1 .

Table 1: Schedule of Events

Assessment	Study Period / Frequency of Assessments								
	Treatment Period						Follow-up		
	Week 14 in Parent Study/ Week 1 in Current Study ^{1,2,3}	Weekly (W2, W3, etc)	Monthly (Q4W) (Week 4, 8, etc)	Every 6 weeks (Q6W) (Week 6, 12, etc)	Every 3 Months (Q12W) (Week 12, 24, etc)	Every 6 Months (Q24W) (Week 24, 48, etc.	1-week F/U	4-week F/U	12-week F/U
Visit Window (days)	-	±3D ⁴	±3D ⁴	±3D ⁴	±5D ⁴	±5D ⁴	±3D	±3D	±5D

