3.2.2. Muscle Effects

Muscle strength and function will be evaluated by the following:

- Muscle disease burden on lower extremity skeletal muscle MRI.
- Muscle strength, based on manual muscle testing (MMT).
- Upper and lower extremity muscle function, based on the Brooke and Vignos scales, respectively.

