8.4.1.2. Muscle Surveillance Magnetic Resonance Imaging

MRI is a non-invasive method that can be applied to the study of skeletal muscle tissue, not only for assessment of anatomy and structure, but also to assess aspects of muscle pathophysiology, including inflammation and fatty infiltration^{41,51,52} in muscular dystrophy patients. MRI will be performed in this study to evaluate changes in lower extremity muscle disease burden following treatment with ATYR1940, based on changes in inflammation within skeletal muscle tissue.

Patients without contraindications for MRI (e.g., metal prosthesis or pacemaker, per site MRI protocol, as well as those with disease features precluding ability to perform MRI) will undergo a lower extremity skeletal muscle Surveillance MRI examination at the time

points designated in [Table 1](#). Imaging will be performed locally at each site, using either 1.5 or 3.0 Tesla Siemens or Philips scanner, based on a protocol provided in the Imaging Acquisition Protocol. The MRI scans will be formatted to acquire multiple acquisition sequences, including T1 and STIR.

Images will be reviewed and interpreted by a central reader with expertise in muscle MRI, as outlined in the Imaging Acquisition Protocol. For each time point, muscle inflammation will be assessed based on the presence or absence of STIR hyperintensity, and fat infiltration on T1-weighted sequences will be graded using the Fischer score. [Wattjes, Kley, Fischer](#) ⁵³

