9.2.10. Pharmacodynamic Analyses

9.2.10.1. Lower Extremity Skeletal Muscle MRI

Surveillance MRI of both of muscles in both of the lower extremities will be performed to assess muscle disease burden. At each time point, muscle inflammation will be assessed based on the presence or absence of STIR hyperintensity, and fat infiltration on T1-weighted sequences will be graded using the Fischer score.⁵³

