1.1 Changes from Protocol

The ATYR1940-C-006 Protocol dated 22-Mar-2016 defines baseline as the following: For patients who received ATYR1940 \leq 4 weeks previously in the parent study, baseline refers to the baseline in the parent study (i.e., the most recent assessment obtained before the first study drug dose). For patients who received ATYR1940 >4 weeks previously in the parent study, baseline refers to assessment obtained before the first ATYR1940 dose at Week 1 in the current study.

However, the SAP defines baseline as the baseline in the parent study (ATYR1940-C-003 or ATYR1940-C-004) for all subjects enrolled in study ATYR1940-C-006.

The following changes/clarifications were provided for the schedule of events in Table 1 of the protocol:

- Plasma Biomarkers- Time points for Plasma Biomarkers were not specified in the protocol: During all dosing visits Plasma Biomarkers should be collected at infusion pre dose and 4 hours after the start of the infusion.
- Muscle Biomarker- Muscle Biomarkers are being completed at Week 14 in the 004 parent study; however, the 006 protocol says that these procedures will be completed in addition to Week 14 procedures. Muscle biomarkers are not completed in the 003 study: Muscle Biomarker should be drawn during the Week 1 visit in the 006 study for 003 patients only as patients in the 004 study will have muscle biomarkers collected at the Week 14 visit in the parent study, which occurs on the same day.
- Plasma Complement Factors- Plasma Complement Factors are requested to be collected during Week 1 in the 006 study; however, plasma complement factors are already being collected during the Week 14 visit in the parent study, which occurs on the same day: Collection of plasma complement factors is not required to be repeated during the Week 1 extension visit as noted in the Schedule of Events.
- Serum Complement & Tryptase Levels- Serum Complement & Tryptase Levels are requested to be collected during Week 1 in the 006 study; however, Serum Complement & Tryptase Levels are already being collected during the Week 14 visit in the parent study, which occurs on the same day: Collection of Serum Complement & Tryptase Levels is not required to be repeated during the Week 1 extension visit as noted in the Schedule of Events.

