4.2 Pharmacodynamic Variables

4.2.1 Muscle Surveillance Magnetic Resonance Imaging (MRI)

Magnetic resonance imaging (MRI) will be performed during the study to evaluate changes in lower extremity muscle disease burden following treatment with ATYR1940. Patients without contraindications for MRI will undergo a lower extremity skeletal muscle surveillance MRI examination at Week 1, every 3 months (Week 12, 24, etc), and 12-Week post-treatment follow-up or early termination. Images will be reviewed and interpreted by a central reader. Central readers will perform the following:

- Review the surveillance scan of the lower extremity muscles
- Determine the short tau inversion recovery (STIR) positive muscles and indicate:
 - STIR signal status (Yes for baseline, and Yes/No for follow-up)
 - Side of the body (right or left)
 - Name of the muscle (various)
 - Region of the muscle (proximal, middle, or distal)
- Use T1 image scores from the STIR positive muscles to determine presence of fatty infiltration using the Fischer score for scoring:

Fischer Scale	Description
• Grade 0	Normal appearance
• Grade 1 (mild)	Presence of traces of increased signal intensity on the T1-weighted MR sequences
• Grade 2 (moderate)	Presence of increased T1-weighted signal intensity with beginning confluence in less than 50% of the muscle
• Grade 3 (severe)	Presence of increased T1-weighted signal intensity with beginning confluence in more than 50% of the muscle
• Grade 4	End-stage appearance; entire muscle replaced by increased density of connective tissue and fat
• NA	Not a STIR positive muscle

- Prioritize the STIR positive muscles found in the baseline scan for each patient based on both the STIR hyperintensity and Fischer score (must be 3 or less).

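### No planned output reports MRI change from the SAP's own baseline: the only MRI listing is confined to 006 data, while baseline lies in the parent study

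*SAP*

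**What the plan says.** **Endpoint.** The protocol synopsis places MRI under "Changes from baseline in the following clinical parameters", as "Muscle disease burden on lower extremity skeletal muscle MRI". Protocol 3.2.2 repeats the item without the change-from-baseline lead-in. Protocol 8.4.1.2 gives the purpose: "MRI will be performed in this study to evaluate changes in lower extremity muscle disease burden following treatment with ATYR1940". SAP 4.2.1 gives the same purpose, "to evaluate changes in lower extremity muscle disease burden following treatment with ATYR1940".

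**Baseline.** SAP 1.1 declares a departure from the protocol: "the SAP defines baseline as the baseline in the parent study (ATYR1940-C-003 or ATYR1940-C-004) for all subjects enrolled in study ATYR1940-C-006". SAP 6.0 repeats it with no exception for MRI.

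**Output.** SAP 9.7.1 plans this and nothing else for MRI: "A listing will be generated from the surveillance MRI data showing the STIR positive muscles". Appendix 4 and the shell title it Listing 16.2.18, on Safety Population 006. SAP 5.1 restricts that population to 006 data; SAP 5.2 defines a Cumulative population with the same patients plus their parent-study data.

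**Reading rule.** Protocol 9.2.10.1 says "At each time point, muscle inflammation will be assessed based on the presence or absence of STIR hyperintensity", and protocol 8.4.1.2 says "fat infiltration on T1-weighted sequences will be graded using the Fischer score". Neither attaches a STIR condition to the fat grading. SAP 4.2.1 scores the STIR-positive muscles and codes the rest NA. SAP 1.1 does not list this among its changes.

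**The concern.** An endpoint defined as a change needs a reference scan and follow-up scans in the same output. Here the SAP puts the reference in one dataset and builds the only MRI output from another. Anyone who later wants the MRI change must choose the reference scan by hand, after the images have been read, in an uncontrolled study where a favourable choice would be hard to detect. MRI is also the one muscle-effect measure that looks directly at inflammation and fat in the muscle, so it bears closely on the trial's question about biological activity.

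**Working it through.** No formula applies: the study is descriptive, with no hypothesis test and no calculated sample size. The check sets the planned outputs side by side (SAP Appendices 4 and 5).

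| Measure | By-visit table | Listing | Listing population | Baseline used | Change shown |
|---|---|---|---|---|---|
| MRI | none | 16.2.18 | 006 | none named | no |
| Manual muscle testing | 14.3.1 | 16.2.19 | Cumulative | parent | yes |
| Brooke/Vignos | 14.3.2 | 16.2.20 | Cumulative | parent | yes |
| INQoL | 14.3.3 | 16.2.21 | Cumulative | parent | yes (listing: overall score only) |
| FSHD-HI | 14.3.4 | 16.2.22 | 006 | 006 Week 1 | yes |

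1. **Tables.** MRI is in 0 of the 4 pharmacodynamic tables. SAP 9.7.2, which names the variables given change summaries, leaves it out.

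2. **Listings.** Of 5 pharmacodynamic listings, 3 are Cumulative and 2 are 006-only. Of those 2, FSHD-HI names 006 Week 1 as its baseline. So 1 of 5, MRI, has neither parent data nor a named 006 baseline. Its shell has 8 columns, none for change.

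3. **Other plans.** The PK/PD SAP mentions MRI only for possible post-hoc correlations, and its output list has no MRI item.

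4. **Would the protocol's own baseline rule help?** Mostly not. Protocol 9.2.1 uses the parent baseline when the last parent dose was at most 4 weeks earlier. The usual maximum gap is 3 weeks, and 3 ≤ 4, so only exceptional patients would have a Week 1 baseline. Protocol 9.2.1 also says that parent and extension data are to be combined, which a 006-only listing does not do.

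5. **Is the entry scan in 006 data?** Footnote 1 of the schedule (Table 1) distinguishes procedures done at extension Week 1 from those done at parent Week 14. The MRI cell carries a plain X. FSHD-HI and others carry the superscript 1. The five assessments that SAP 1.1 discusses as Week 1 additions to the parent visits (muscle biomarkers, plasma complement, serum complement with tryptase, visual acuity, audiometry) all carry the superscript, which supports reading it as marking the extension's own procedures. SAP 9.7.1 also makes the Week 1 MRI conditional on being required. So the entry scan appears to be parent Week 14 data, and a strictly 006-only listing could first show MRI at Week 12. The cell borders that would settle this are not visible in the text available.

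6. **Fischer grading.** SAP 4.2.1 does not say whether NA is applied visit by visit or only to muscles that were not STIR-positive at baseline. Under the first reading, a muscle that loses its STIR signal also loses its follow-up fat grade.

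**The case against.** The strongest reply is that the plan never promised more. MRI sits under an exploratory objective. Protocol 9.2.10.1, the MRI analysis section, promises assessment and grading at each time point rather than a change summary. STIR status and Fischer grade are per-muscle categories, no composite burden score is defined, and up to 24 patients are expected with no testing. SAP 4.2.1 lists scans from Week 1 and then speaks of baseline and follow-up, so Week 1 may be the intended MRI baseline.

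Part of this stands. It limits the weight of the point and argues against inventing a burden score. It does not close the gap. The synopsis endpoint is a change, and the Muscle Effects group is not labelled exploratory, whereas quality of life is and still receives change tables. Categorical data can be shown as shifts. A Week 1 baseline would contradict SAP 6.0 and, on step 5, may itself lie outside the listing.

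A reader might infer that the Fischer rule erases fat-grade change whenever inflammation resolves. The documents do not support that. SAP 4.2.1 records follow-up STIR status as yes or no and gives priority to muscles found positive on the baseline scan, which suggests that those muscles stay in the data. The protocol also leaves reading details to an Imaging Acquisition Protocol that is not among the documents. The missing SAP 1.1 entry is, by itself, editorial.

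**Conclusion.** The gap is real and worth closing, at low cost. Change in MRI burden from the SAP's stated baseline appears in no planned output, and it is the only one of the three muscle-effect measures so placed.

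A reader might go further and infer that no MRI change can be seen at all. That is too strong: change between 006 scans can be read by hand from the listing. Nor do the documents show that any result would be biased.

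The conclusion rests on two points that the documents do not settle. One is that a parent baseline surveillance scan exists for each patient: the parent MRI schedule is not given, although SAP 4.2.1 refers to a baseline scan and the Listing 16.2.18 footnote to a targeted scan. The other is that the Week 1 scan belongs to parent Week 14, which affects only the further point about the entry scan. The frequency of STIR changes is not given either, so no effect on results can be quantified.

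**What to change.** 1. Put Listing 16.2.18 on Safety Population Cumulative, so that parent baseline and Week 14 scans are included. If a parent baseline scan is unavailable or not comparable, name the parent Week 14/006 Week 1 scan as the MRI baseline in SAP 6.0. That choice also needs the Cumulative listing.

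2. Add one descriptive by-visit table from data already recorded: for muscles STIR-positive at baseline, the shift in STIR status (yes to yes or no) and in Fischer grade. Report newly positive muscles separately, because a count over a set fixed at baseline can only stay the same or fall and would look like improvement.

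3. State in SAP 4.2.1 whether NA applies per visit or only to muscles not STIR-positive at baseline. Use follow-up grades where they were recorded and report the others as missing, without re-reading scans. If NA was applied per visit, some grades will not exist and this step will not recover them. List the STIR restriction in SAP 1.1; this is secondary.

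The cost is one listing re-run, one added table, and a check that parent and 006 reads are comparable. SAP 1.0 provides for a final version before database lock. If lock has passed, protocol 9.3 requires the change to be documented in the clinical study report.
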